4.17 Will any external monitors require access to this study in Epic?

No

4.19 Mark all that apply to your study:

1. Protocol

1.1 Is there a separate, written protocol that will be submitted in addition to this form? (Note: a grant application is not considered to be a protocol)

No

1.2 Select up to three key words below that best describe this research study:

- Psychology
- Clinical

1.3 Provide a short summary/abstract of the purpose and procedures of the study proposed in this IRB application.

- DO NOT include information on studies not proposed in this application.
- Use LAY terminology only. This must be easily understandable by IRB community members and nonscientists.
- DO NOT cut and paste technical abstracts from source of support applications that may not be understood by a general audience.

This project focuses on understanding the cognitive and neural mechanisms by which mindfulness training (MT) results in positive behavioral change and enhanced psychological well-being. Building upon research by the Human Connectome project and the Dual Mechanisms of Cognitive Control studies, we will recruit MZ and DZ twins and non twin siblings, to participate in fMRI sessions.

The subjects will be recruited in pairs, with one subject randomly assigned to the MT condition (mindfulness-based stress reduction, or MBSR; the most-validated and standardized form of MT instruction) and the other serving as a (wait-list) control. Each co-subject will undergo extensive behavioral and MRI neuroimaging assessments in a pre/post fashion, before and after the MT (or no-contact control) intervention, to test for specific MT-related effects.

1.4 Specify your research question(s), study aims or hypotheses:

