We will use this design to investigate theoretically-focused hypotheses that stem from our guiding framework regarding the neural mechanisms of cognitive control. Specifically, using a newly developed cognitive control task battery, we will test the counterintuitive hypothesis that MT produces an enhancement in the neural mechanism and circuits associated with reactive (rather than proactive) control. An additional subset of MZ twin participants will undergo retesting with the original HCP protocol, in order to provide a comprehensive assessment and comparison of MT effect sizes across multiple domains of cognitive and brain function. Success in this project will have high relevance for public health, by providing innovative experimental tools and a novel theoretical framework from which to empirically evaluate and better understand the potential impact of MT programs as lifestyle interventions for enhancing psychological well-being in healthy populations.

1.5 Background and significance and/or Preliminary studies related to this project:

Over the last decade, current understanding of the neural basis of complex psychological functions has shifted in emphasis from a focus on specific regions, to that of brain networks, while still highlighting the importance of key nodes within these networks. In terms of attentional and cognitive control, the lateral frontoparietal network(FPN) is generally agreed to be paramount. Within the FPN, dorsolateral prefrontal cortex (dIPFC) regions appear to function as critical hub nodes.

Strikingly, current cognitive neuroscience research has also associated MT with critical changes to each of these networks and key nodes. The FPN, and dIPFC in particular, show MT-related effects that appear to reflect both the state-changes associated with increased focusing of attention during meditative states, as well as potentially trait-related changes due to MT experience that result in more effective utilization of this network during attentional control tasks.

Building upon MZ and DZ research conducted by the HCP and current R37 study on dual mechanisms of cognitive control by [name], we will utilize the tasks and build upon the data of these successful and ongoing studies.

1.6 Literature cited/references (if attaching a grant enter N/A):

N/A

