1.7 Describe EACH of your participant populations

- Include description of any control group(s)
- Specify the Inclusion/Exclusion criteria for EACH group

Participants are healthy young adults of age range 18 to 45 years, native English speakers with no contraindication for fMRI.

We will recruit a cohort of monozygotic (MZ) and dizygotic twins and siblings from Missouri family registries. We will target individuals that have completed study 201510077, Dual Mechanisms of Cognitive Control.

Any participant will be excluded for the following reasons: 1) taking any medication with potential cognitive effects (e.g., sleeping pills); 2) taking any psychotropic medications; 3) the presence of any clinically unstable medical disorder, or a medical disorder that affects cognitive or motor function (e.g., epilepsy, Parkinson's Disease); and 4) present or past head injury with documented neurological sequelae, and/or causing loss of consciousness. Additionally, subjects for the fMRI studies will also be excluded for: 1) pregnancy; 2) history of claustrophobia; 3) non-medically approved metallic objects in the body; and 4) history of heart rhythm abnormalities or presence of a heart pacemaker.

In addition, we will screen for premature births (for twin pairs, before 34 weeks; for other siblings, before 37 weeks, to avoid inclusion of individuals with atypical connectivity patterns resulting from very premature birth.

1.8 Check all materials/methods that will be used in recruiting participants:

- Telephone script
- Ads/Brochures/Posters/News Release/Fliers
- Email or letters
- Other Materials - prior participants in study 201510077 ([name], PI) Dual Mechanisms of Cognitive Control
- Existing Registry/database
 - Other Research Study - prior participants in study 201510077 ([name], PI) Dual Mechanisms of Cognitive Control
 - Other Existing Registry/database - Missouri Family Registry (twin database)
- Medical Records or Other PHI

Attachment Name	Category	Version	Date Attached
DMCC_MBSR_EMAIL.rtf	Recruitment: Other	1	05/02/17
priorparticipantflyer.rtf	Recruitment Materials: Ads/Brochures/Posters/News Release/Fliers	1	05/15/17
newparticipantemailflyer.rtf	Recruitment Materials: Ads/Brochures/Posters/News Release/Fliers	1	05/15/17

1.8.a List the individual data elements you will need to access/use from the patient or clinic records to identify potential participants for recruitment

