For the telephone screen, we are generating PHI in the form of medical history and medications (see attached phone screen document).

1.8.b What is the plan for participant identifiers obtained to identify participants for recruitment?

Identifiers for those who do NOT enroll will be destroyed at the earliest opportunity, consistent with the conduct of the research (for example when recruitment and enrollment are completed.)

1.8.c Does the research team agree that the requested information will not be reused or disclosed to any other person or entity, except as required by law, for authorized oversight of the study, or for other research for which the use or disclosure of the requested information would be permitted by the HIPAA Privacy Rule?

Yes

1.9 Will you use a screening log or other record that would include information on people who do not consent to participate in the study?
No

1.10 Describe where the consent discussion will occur (check all that apply):

- Private room or area
- By phone

1.11 Participants and/or their legally authorized representative will have (check all that apply to the consent process and explain process in Question 1.12 below):

- As much time as they desire to consider enrolling in the study, including:
 - An opportunity to thoroughly review the consent materials with knowledgeable members of the research team, and with family and/or friends as appropriate
 - Sufficient time to have all of their questions answered

1.12 Provide a description of the enrollment and consent process in sequential order and address EACH of the bulleted points below:

- Describe each study population separately including control population
- Describe when recruitment and consent materials are used
- Indicate how much time individuals will have to consider participation
- Use THIRD person active voice. For example, "the principal investigator will identify potential participants, the study coordinator will discuss the study with participants over the telephone and schedule the first study visit, etc..."
- Describe the steps that will be taken by the research team to minimize the possibility of coercion or undue influence during the consent process

We will recruit healthy young adult twin pairs. We will utilize the Missouri Twin registries.

Email: An email will be sent to former DMCC participants about the study.

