A. Intake: This will involve a brief interview and data on standard physiologic information (height, weight, blood pressure, and pulse). If blood pressure is considered high, participant will be given an information sheet at the end of their session. All participants will then be administered the MRI screening form and demographic form. If participant is deemed eligible, the experiment will commence. If they are ineligible, they will be told why and will be withdrawn from the study.

B. Behavioral Practice Session (This will take approximately 2 hours.)

1. TASKS: Participant will complete 4 behavioral tasks (AXCPT, Stroop, Sternberg and Taskswitching) on a computer. Subjects will complete the Operational and Symmetry Span tasks, an 18 item Ravens Matrices task, a breath counting task, and a Letter Set task.

2. Questionnaires:

Subjects will also complete behavioral questionnaires during practice sessions, which include: Behavioral Inhibition System/Behavioral Approach System (BIS/BAS)

Need for Cognition Scale (Nfc)

Generalized Reward and Punishment Expectancy Scales (GRAPES)

Mindful Attention Awareness Scale (MAAS)

Five Facet Mindfulness Questionnaire (FFMQ)

Pittsburgh Sleep Quality Index

State Trait Anxiety Inventory (STAI)

Domain Specific Risk Taking(DOSPERT)

The Positive and Negative Affect Schedule(PANAS)

Sensitivity to Reward and Punishment Questionnaire

Self-Scoring Self Control Scale (SSC)

Barratt Impulsiveness Scale (BIS)

Alcohol&Smoking Questionnaire

Neo FFI

Fordyce

Patient health questionnaire (PHQ0

Satisfaction with Life (SWL)

Self Compassion scale (scmp)

Pittsburgh sleep quality index (PSQI)

Exit Satisfaction Survey

pre & post task questionnaires

C. Break

D. Scanning: In the scanner, participants will perform baseline session of the 4 tasks (AXCPT, Stroop, Task-switching and Sternberg) in a scanner. This will take approximately 2 hours. Blood pressure and pulse will be measured prior to scan. Scanning will consist of structural, functional and resting state acquisition.

E. Review of schedule for Scanning Session II.

Session II and Session III (can either be completed on the same day or broken into two sessions A&B&D, A,C,D):

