A. Behavioral Practice Session: Participant will complete 4 behavioral tasks (AXCPT, Stroop, Sternberg and Task-switching) on a computer. Participants will practice the corresponding (counterbalanced order of proactive/reactive) condition of the tasks outside of the scanner before the scanning sessions. These practice sessions will last approximately 30 minutes each. If not completed, subjects will complete any questionnaires remaining from Session I Behavioral Practice.

B. Scanning Sessions:

Participant will perform two scanning sessions in Session II of the study. The sessions will be counterbalanced between the proactive and reactive conditions of the four tasks (AXCPT, Stroop, Task-switching and Sternberg) in a scanner. Scanning will consist of both functional (tasks) and resting state acquisition. Each scan will last approximately two hours. Blood pressure and pulse will be measured prior to the scan.

B: Break

C. Second Scanning Session (of counterbalance)

D. Exit Survey (post-task questionnaire)/Debriefing

One of the twin participants will be randomly selected to participate in an 8-week Mindfulness-based stress reduction (MBSR) program led by certified MBSR instructors at a dedicated facility, supervised by [name]. The MBSR program uses a combination of mindfulness meditation, body awareness, and yoga to help people become more mindful. The MBSR program is an eight-week workshop taught by certified trainers that entails weekly group meetings (two-hour classes) and a one-day retreat (six-hour mindfulness practice) between sessions six and seven, home practice, and instruction in three formal techniques: mindfulness meditation, body awareness, and simple yoga posture.

After the completion of the program, the twins will return for sessions three and four - a repeat/retest of Session I and II.

If participants that have completed or are enrolled in IRB 201510077, Dual Mechanisms of Cognitive Control ([name], PI), they will not complete session one and two. They will be asked to begin at the mindfulness training and complete sessions three and four.

The twin that was not chosen to participate in the MBSR initially will be given the opportunity to voluntarily participate after the completion of the retest sessions.

Task descriptions:

AXCPT:

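### The waiver of Sessions I and II covers people who are only enrolled in the earlier, ongoing study, so someone could start training or the wait-list period without a finished pre-training assessment

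*Protocol*

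**What the plan says.** The operative rule stands in Protocol section 1.13, after the description of the MBSR programme. It opens "If participants that have completed or are enrolled in IRB 201510077, Dual Mechanisms of Cognitive Control" and continues "they will not complete session one and two. They will be asked to begin at the mindfulness training and complete sessions three and four". Either status, completed or merely enrolled, triggers the waiver.

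Four other places bear on it:

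- Section 1.3 (summary) states the design: "Each co-subject will undergo extensive behavioral and MRI neuroimaging assessments in a pre/post fashion, before and after the MT (or no-contact control) intervention".
- Section 1.5 (background) refers to the "current R37 study on dual mechanisms of cognitive control" and says "we will utilize the tasks and build upon the data of these successful and ongoing studies".
- Section 1.7 (populations) says "We will target individuals that have completed study 201510077, Dual Mechanisms of Cognitive Control".
- Section 1.12 (enrolment and consent) says "An email will be sent to former DMCC participants about the study".

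Section 1.13 also describes the sessions after the programme as a retest of Sessions I and II, so those two sessions are the pre-training measure.

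**The concern.** The trial asks whether training changes behaviour and brain function, and it measures this before and after within randomised pairs. A waiver of the first assessment is harmless if equivalent data are already held. This waiver depends on enrolment status in another study, not on data being held, and that other study is still active. For people who have finished it, the words about being enrolled add nothing. They matter only for people who have not finished, and these are the people for whom a skipped baseline is a real loss.

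A pre-training measure that was not taken before training cannot be recovered by any later analysis plan. If one co-subject lacks it, the pair's difference in change cannot be computed, even when the other co-subject has a full baseline.

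**Working it through.** The point rests on the text. The protocol gives no figure to reproduce for it.

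**Step 1: who is exempt.** Section 1.13 exempts anyone who has completed, or is enrolled in, study 201510077.

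**Step 2: can an enrolled person be untested or partly tested?** Section 1.5 calls the earlier study current and ongoing, so such people can exist. The protocol does not say how many.

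**Step 3: is there a safeguard elsewhere?** No sentence makes completed earlier sessions a condition of the waiver. Section 1.5 speaks of building on earlier data, but as background and not as an entry condition.

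**Step 4: side by side.**

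| Protocol section | Scope |
|---|---|
| 1.3 | every co-subject assessed before and after |
| 1.7 | targets people who have completed the earlier study |
| 1.12 | email to former participants |
| 1.13 | waiver for completed **or enrolled** |

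Section 1.13 is wider than 1.7 and 1.12 and, followed literally, can break 1.3.

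**Step 5: direction of the effect.** Whether a person is exempt depends on status in another study, and allocation within the pair is random. A pair left out of the change analysis removes one person from each arm. A pair with only post-training data still gives a randomised contrast. No bias toward either arm is expected.

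**Step 6: one illustration of scale.** Only the 50 participants come from the protocol (section 2.1.a); taken as 25 pairs, this assumes that all enrol in pairs and are analysed. Everything else is assumed: two-sided 5% test, standardised effect d = 0.5, within-pair correlation r = 0.3, pre/post correlation rho = 0.7, and pairs without complete baseline dropped from a pre/post change analysis.

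- Variance of the within-pair difference in change, taking r to apply to change scores as well: 2(1 − r) × 2(1 − rho) = 1.4 × 0.6 = 0.84, so SD = 0.9165.
- Standardised within-pair effect: 0.5 / 0.9165 = 0.5455.
- Noncentrality: 0.5455 × √n, with n − 1 degrees of freedom.

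| Usable pairs | Noncentrality | Power |
|---|---|---|
| 25 | 2.728 | about 74.5% |
| 23 | 2.616 | about 70.6% |
| 20 | 2.440 | about 63.9% |

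The losses are about 3.9 points for two pairs and 10.6 points for five. An analysis that keeps the post-training data of such pairs would lose less. The figures of 23 and 20 are not predictions.

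**The case against.** The strongest reply is that the sections, read together, show an obvious intent. Section 1.3 requires assessment before and after, section 1.5 relies on the earlier study's data, and a retest in section 1.13 presupposes a first test. On this reading the waiver spares people a repeat of scans done under the earlier study, and the enrolled are those now passing through it. Recruitment in sections 1.7 and 1.12 is aimed at completers and former participants, so few others should arrive. This is fair as to intent and exposure. It does not remove the gap: the rule that staff would follow still allows entry without the data, and no sentence prevents it.

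The following stronger readings are tempting but not supported.

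- **That baselines are missing for everyone who comes from the earlier study.** People who completed the corresponding sessions are not in question.
- **That people are randomised without a baseline.** Section 1.13 does not fix when randomisation takes place. It says only that exempt people begin at the training, so the safe statement concerns the start of training or of the wait-list period.
- **That particular Session I measures will be lacking.** A reader might point to "Subjects will complete the Operational and Symmetry Span tasks, an 18 item Ravens Matrices task, a breath counting task, and a Letter Set task". Whether the earlier study collected these depends on a protocol that is not shown.
- **That a substantial loss of power is established.** No rate of affected people is given, and a partly tested person would still hold some baseline data.

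**Conclusion.** The point holds as a defect in an operative rule. The waiver is wider than the recruitment text, conflicts with the stated design, and could lose data that cannot be recovered. It goes beyond missing detail, because the rule as written tells staff to skip the assessment.

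Its size is not known and may be small. The harm is limited to lost within-pair change data and some precision. The power figures show only how quickly precision would fall if a few pairs were lost, under the assumed d, r and rho. The conclusion does not depend on them. Correction is worthwhile because prevention is cheap and the loss, where it occurs, is permanent. The validity of the randomised comparison is not called into question.

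**What to change.** Reword the rule in section 1.13, for example: *Sessions I and II are waived only for a participant who has completed the corresponding sessions of study 201510077 (baseline, proactive and reactive) before the pair is randomised and training starts. Otherwise that participant first completes the missing sessions in this study.* This brings section 1.13 into line with sections 1.3, 1.7 and 1.12. A co-subject who has already been tested repeats nothing.

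The cost is one reworded rule, plus scanner time and a delay for any affected pair. By the durations in section 1.13, the most that one person could need is three scans of about two hours (3 × 2 = 6 scanner hours) and about 3 hours of practice (2 hours in Session I plus two sessions of 30 minutes). It is less where some earlier sessions are done.

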1.14 Will participants be randomized?
Yes

1.15 Will any of the following be used to collect information from the participant or others?

- Screening questions or screening/eligibility questionnaires
- Surveys
- Questionnaires
- Stimuli
- Any other written assessments

Yes

Attachment Name	Category	Version	Date Attached
FFMQ_full.pdf	Subject Data Collection Instruments	1	01/17/17
BIS11English.pdf	Subject Data Collection Instruments	1	01/17/17
STAI.pdf	Subject Data Collection Instruments	1	01/17/17
Dospert.pdf	Subject Data Collection Instruments	1	01/17/17
Intake_PSQI_EON(1).pdf	Subject Data Collection Instruments	1	01/17/17
PANAS.pdf	Subject Data Collection Instruments	1	01/17/17
Exit_Satisfaction_Survey_NMM.doc	Subject Data Collection Instruments	1	01/17/17
MBSR-Alcohol.doc	Subject Data Collection Instruments	1	01/17/17
BISBAS.pdf	Subject Data Collection Instruments	1	01/17/17
ncogscale.pdf	Subject Data Collection Instruments	1	01/17/17
GRAPES-typed-clean.doc	Subject Data Collection Instruments	1	01/17/17
BJH_MRI-Screening_B1_208-3343-2292_20EF_Proof.pdf	Subject Data Collection Instruments	1	01/17/17
01092013_briefscc.pdf	Subject Data Collection Instruments	1	01/17/17
NMM_pre and post task.docx	Subject Data Collection Instruments	1	01/17/17
sprs (1).pdf	Subject Data Collection Instruments	1	01/17/17
MAAS trait research-ready + intro.pdf	Subject Data Collection Instruments	1	01/17/17
SWL.pdf	Subject Data Collection Instruments	1	08/14/17
fordycescale.pdf	Subject Data Collection Instruments	1	08/14/17
PHQ.pdf	Subject Data Collection Instruments	1	08/14/17
DEMOGRAPHIC FORM (2).docx	Subject Data Collection Instruments	1	01/25/17
NEO-FFI.pdf	Subject Data Collection Instruments	1	08/14/17
PSQI.pdf	Subject Data Collection Instruments	1	08/14/17
sComp.pdf	Subject Data Collection Instruments	1	08/14/17

1.16 Does this project involve creating any audio, video, or photographs?
Yes

1.17 Does the study include any form of deception (e.g., providing participants with false information, misleading information, or withholding information about certain study procedures)?

Examples:

- Procedure includes a cover story that provides a plausible but inaccurate account of the purposes of the research.
- Participants will be provided with false information regarding the particular behaviors of interest in the research.
- Procedures include a confederate pretending to be another participant in the study.
- Participants will be told that the research includes completion of a particular task, when in fact, that task will not be administered.
- Study is designed to introduce a new procedure (or task) that participants are not initially told about.

No

